### **3.3 Adaptive Design**

Adaptive design is not planned for this study. One of the goals of this study is to replicate a previously completed trial. Therefore, the study will continue to its expected completion without adaptive design elements.

## **4. Covariates and Subgroups**

### **4.1 Planned Covariates**

The planned covariates include the baseline stratification factors as well as other important baseline factors:

- Screening serum PTH level (< 900 pg/mL,  $\geq$  900 pg/mL)

- Screening serum cCa level (< 9.0 mg/dL,  $\geq$  9.0 mg/dL)
- Country (China and non-China)
- Dialysis vintage (0 - $\leq$  1 yr, > 1- $\leq$  5 yr, > 5 yr)
- Dialysate calcium (< 3.0 mEq/L vs.  $\geq$  3.0 mEq/L)
- Baseline vitamin D sterol use (yes/no)
- Baseline calcium containing phosphate binder or calcium supplement use (yes/no).
- Previous cinacalcet use (yes/no)
- Sex (male/female)
- Age (< 65 years,  $\geq$  65 years)

All of these covariates will be used in the Multiple Imputation Method to be implemented in sensitivity analyses of the key secondary endpoint of achievement of > 50% and > 30% reduction from baseline in mean predialysis serum PTH during EAP, respectively.

#### **4.2 Subgroups**

The secondary efficacy endpoints will be analyzed in the subgroups defined by baseline covariates listed in [Section 4.1](#).

### **5. Definitions**

#### **5.1 Study Time Points**

##### Informed Consent Date

The informed consent date for each subject is the date the subject signs the original informed consent for this study.

##### Screening Phase

The period after a subject has provided written informed consent and prior to randomization. This period may last up to 8 weeks and it is during this period when eligibility is determined, based on all screening tests and procedures.

##### Enrollment Date

The date a subject is randomized to a treatment group by the interactive voice/web response system (IXRS) after they have satisfied all enrollment criteria.

##### Randomization Date

The randomization date is the same as the enrollment date.

### Study Week

The 7-day periods beginning with Study Day 1.

### Study Day 1

The first day that investigational product is administered to the subject. For subjects who did not receive any investigational product during the study, Study Day 1 will be the randomization day.

### Study Day

For each subject and for a given study visit date, study day is defined as the number of days since Study Day1:

$$\text{Study day} = (\text{study visit date} - \text{Study Day 1 date}) + 1$$

If the date of interest is prior to study day 1, study day will be calculated as

$$\text{Study day} = (\text{study visit date} - \text{Study Day 1 date}).$$

### Efficacy Assessment Phase (EAP)

The period between Week 20 and Week 27, inclusive.

### Date of Last Dose IP Received

For each subject, the last investigational product dose date is defined as the date when the last non-missing dose of investigational product is administered (zero dose is still counted).

### Subject-level End of Study Date

End of study for each subject is defined as the date of the subject last study assessment in the study. The date subject ended the study is recorded on the End of Study electronic case report form (CRF).

### Study-level End of Study Date

End of study for the study is defined as the date when the last subject is assessed or receives an intervention for evaluation in the study (ie. last subject last visit), following any additional parts in the study (ie, long-term follow-up) as applicable.

### Follow-up

The 30-day period that occurs after a subject receives the last dose of investigational product during which safety information will be collected.

## 5.2 Demographics and Baseline Related Definitions

### Age

Age is calculated as the subject's (floor) integer age in years at the enrollment date. If the date of birth is not available, collected age will be used in the analyses.

### Body Mass Index (BMI)

BMI equals a person's weight in kilograms divided by baseline height in meters squared ( $\text{kg}/\text{m}^2$ ).

### Dialysis Vintage (years)

Dialysis vintage is defined as the duration in years from the dialysis start date (recorded on the end-stage renal disease (ESRD) history CRF) to the randomization date.

### Baseline Values

Baseline values of PTH, cCa, and serum phosphorus are defined as the average of the last pre-dialysis assessment done during the screening period and the pre-dialysis assessment done on Study Day 1.

All other baseline laboratory values are using the last non-missing assessment taken prior to or on Study Day 1 (Study Day 1 assessment if available, otherwise the last screening assessment prior to Study Day 1).

Baseline vital sign and weight will be the last post-dialysis assessment values prior to or on Study Day 1.

The use of vitamin D, including nutritional vitamin D (vitamin D supplement) and vitamin D sterol (active vitamin D), is defined as use of vitamin D during the 7 days period prior to Study Day 1, inclusive.

The use of other concomitant medication of interest at baseline is defined as use of each concomitant medication on Study Day 1. This includes medication use that starts prior to Study Day 1 and ends on Study Day 1 or duration of use covers Study Day 1.

### Change from Baseline

The arithmetic difference between a post-baseline value and baseline value for a given time point:

$$\text{Change from baseline} = (\text{post-baseline value} - \text{baseline value})$$

### Percent Change from Baseline

For each subject, percent change from baseline in a given variable at a given time point is defined as:

$$100 \times [(value \text{ at given time point} - \text{baseline value}) / \text{baseline value}]$$

### **5.3 Other Study Related Definitions**

#### Protocol Scheduled Visits

The clinical planned event (CPE) assigned in the clinical database will be used as protocol scheduled visits. If the value at a scheduled visit is missing, an unscheduled assessment can be used provided the unscheduled assessment occurs within the window for that study week, ie

$$\text{ceiling}(\text{study day of the unscheduled visit} / 7) = \text{study week number}$$

All missing scheduled assessments will be replaced using the above method, if possible, prior to deriving any study endpoints.

If the value at a scheduled visit is missing and multiple unscheduled assessments occurs within the window of this visit, or there are multiple values at a scheduled visit, then the first record will be used for the visit.

#### Mean Value of Efficacy Endpoints during the EAP

The mean of the scheduled (including the missing scheduled assessments replaced by unscheduled assessments as described above) pre-dialysis assessments taken during week 20 to week 27, inclusive.

#### Efficacy Endpoints Based on the Percent Changes

Percent change from baseline to the mean value during the EAP for the corresponding endpoint.

#### Corrected Total Serum Calcium (cCa)

$$\text{Corrected calcium (mg/dL)} = \text{Total calcium (mg/dL)} + (4 - \text{albumin [g/dL]}) \times 0.8$$

Total serum calcium will be corrected using above formulae if the serum albumin is < 4 g/dL or 40 g/L, otherwise cCa equals total serum calcium.

### Low Calcium Based on Corrected Calcium Values

cCa values measured by central laboratory will be used to identify cases of low calcium of different severities using the following three categories:

< 7.0 mg/dL, 7.0 - < 7.5 mg/dL, and 7.5 - < 8.3 mg/dL.

### Exposure Period

For each subject who received at least one dose of IP, the number of weeks of IP exposure is calculated as:

Exposure period (weeks) = [(date of last dose received – date of first dose) + 1]/7

### Compliance to Investigational Product (%)

Compliance = number of actual treatments taken / number of prescribed treatments \*100

For the Intravenous (IV) treatment, the number of actual treatments taken is defined as the actual number of IV doses a subject received, and the number of prescribed treatments is defined as the number of IV doses prescribed.

For the oral treatment, the number of actual treatments taken is defined as the number of days that a subject took the oral dose, and the number of prescribed treatment is defined as the number of days that oral treatment was prescribed.

The treatment compliance calculation only considers the periods when a subject was supposed to receive IP and it will exclude the dose withholding periods due to protocol specified reasons on CRF.

### Treatment Emergent Adverse Events (TEAE)

Adverse events (AEs) starting on or after the Study Day 1 as determined by the flag indicating if the adverse event started prior to the first dose of IP on the Adverse Events Summary CRF and up to 30 days after the last dose date. Serious adverse events (SAEs) starting on or after the Study Day 1 as determined by the flag indicating if the adverse event started prior to the first dose of IP on the Adverse Events Summary CRF and up to 30 days after the last dose date.

### Adverse Event Subject Incidence

Defined as the number and percentage of subjects with a reported event(s). For subjects with multiple reports of the same event during the study, the subject will be counted only once. For adverse event tabulations involving severity, the highest severity of the particular adverse events will be used for each subject.

### Adverse Events of Interest (EOI)

Adverse events of interest are defined by the most current standardized product-level event of interest list. Unless otherwise specified, the narrow search scope will be used for all EOIs.

### Concomitant Medications of Interest

The selected medications of interest are: nutritional vitamin D (vitamin D supplement), vitamin D sterol (active vitamin D), calcium supplements, and phosphate binders, as identified in the concomitant medication CRFs.

## **6. Analysis Sets**

### **6.1 Full Analysis Set**

The Full Analysis Set (FAS) includes all randomized subjects. Subjects will be analyzed according to the randomized treatment group assigned by the IXRS. Primary analysis for the primary and key secondary endpoints will be performed using the FAS.

### **6.2 Safety Analysis Set**

The Safety Analysis Set consists of all randomized subjects who receive at least one dose of investigational product. Subjects will be analyzed by their randomized group unless an incorrect treatment was administered throughout the study, in which case the actual received treatment group will be used for analysis. Safety analyses will be performed using the Safety Analysis Set.

### **6.3 Per Protocol Set(s)**

The Per Protocol Analysis Set (PPAS) is defined as all randomized subjects who have no major protocol violations (as defined below) and have at least one post-dose PTH value and had at least 16 weeks exposure of IP. Subjects with the following eligibility deviations will be excluded from the PPAS:

- Less than 18 years at screening
- Not receiving maintenance hemodialysis three times a week for at least 3 months
- Not meeting either calcium concentration or PTH eligibility criteria at screening
- Received cinacalcet within 3 months prior to screening or underwent a parathyroidectomy within 6 months prior to dosing
- Currently enrolling in another study or less than 30 days since ending another study
- Having known sensitivity to either cinacalcet or etelcalcetide

Moreover, subjects who have the following deviations during study period will also be excluded in this analysis set:

- Had parathyroidectomy or kidney transplant before EAP
- Received commercialized cinacalcet during the study
- Missed > 14 consecutive days of intravenous (IV) IP or oral IP, excluding the withholding of IP for protocol-specific reasons

For the subjects who undergo parathyroidectomy or kidney transplantation during EAP, only the PTH values before the surgery will be used.

Subjects in the PPAS will be analyzed according to randomized treatment assignment. PPAS will be used in the sensitivity analysis of the primary endpoint.

#### **6.4 iPTH Completer Analysis Set**

The iPTH Completer Analysis Set (PCAS) includes all randomized subjects with at least 1 predialysis iPTH value during the EAP. Subjects will be analyzed according to randomized treatment group.

#### **6.5 cCa Completer Analysis Set**

The cCa Completer Analysis Set (CCAS) includes all randomized subjects with at least one predialysis cCa value, measured by the central laboratory, during the EAP. Subjects will be analyzed according to randomized treatment group.

### **7. Planned Analyses**

The planned analysis is described as below:

#### **7.1 Interim Analysis and Early Stopping Guidelines**

Interim analysis or early stopping rule are not planned for this study.

#### **7.2 Primary Analysis**

The primary analysis will be the same as final analysis.

#### **7.3 Final Analysis**

After all subjects have completed the study, outstanding data queries have been resolved or adjudicated as unresolvable, and the data have been cleaned and finalized, the study blind will be broken and the final analysis of the data will be performed.

### **8. Data Screening and Acceptance**

#### **8.1 General Principles**

The objective of the data screening is to assess the quantity, quality, and statistical characteristics of the data relative to the requirements of the planned analyses.

## **8.2 Data Handling and Electronic Transfer of Data**

The Amgen Global Study Operations-Data Management (GSO-DM) department will provide all data to be used in the planned analyses. This study will use the RAVE database.

## **8.3 Handling of Missing and Incomplete Data**

Subjects may be missing specific data points for various reasons. In general, data may be missing due to a subject's early withdrawal from study, a missed visit, or non-evaluability of a data point at a particular point in time. Sites will be queried for missing or non-conformant data that are required or considered critical. All efforts will be made to capture complete critical data prior to the database lock.

The following imputation rules will be implemented for critical data if the missing or incomplete data cannot be resolved after the query process:

Only missing or partially missing start dates for adverse events will be imputed with the exception of adverse events occurring prior to the first dose date. Stop dates for AEs will not be imputed. Adverse events with a partially missing start date that is conclusively prior to the date of first IP administered (as indicated by 'Did event start before first dose of IP' on the AE CRF page) will be considered pre-treatment adverse events and excluded from safety analyses. All other partially missing adverse event start dates will be handled as described below, with the reference date being Study Day 1:

- If the year is available and the day and month are missing, the day and month will be set to the 1st of January of the onset year
- If the year and month are available and the day is missing, the day will be set to the 1st of the onset month
- If the day and month are available and the year is missing, the year will be set to the year of the reference date
- If the year and day are available and the month is missing, the month will be set to January of the onset year
- If the resulting date is prior to the reference date, the date will be reset to the reference date (this applies to AE start date imputation only)

Partial/missing start dates for concomitant medications will be imputed using the algorithm above with the reference date being Study Day 1. Partial/missing stop dates for concomitant medications will be imputed using the following logic:

- If the medication stop date is completely missing, then the stop date is set as the end of the study date. Otherwise,

- If the stop year is available and stop month and day are missing, the month and day will be reset to 31st of December of the stop year
- If the stop year and month are available and the stop day is missing, the stop day will be set to the last day of the month of the stop year
- If the stop year and day are available and stop month is missing, the stop month will be set to December of the stop year
- If the stop month and day are available and stop year is missing, the stop year will be reset to the year of the start date
- If any of the resulting dates are prior to the start date, the stop date will be reset to the start date

If any of the resulting dates are after the end of study (EOS) date, the stop date will be reset to the EOS date. Handling of missing laboratory values is described in [section 9.5.1](#) and [9.5.2](#).

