7.3.6 Medication History

The subject's medications at screening (signing informed consent) will be recorded on the eCRF. If the subject is not taking any calcium supplements, phosphate binders, or vitamin D sterols at screening, then the last use should be recorded. If there is previous use of cinacalcet, then the most recent use should be recorded.

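### SAP 8.3 imputes medication dates to the widest window without regard to known prior or on-study status, so some known non-users and on-study starters are classed as baseline users

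*SAP*

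**What the plan says.** SAP 8.3 applies its date rules only where the query process has not resolved the gap. For medication stop dates:

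- Fully missing: "If the medication stop date is completely missing, then the stop date is set as the end of the study date".
- Year only: "If the stop year is available and stop month and day are missing, the month and day will be reset to" 31 December.
- Day missing: "the stop day will be set to the last day of the month of the stop year".
- Month missing: "the stop month will be set to December of the stop year".
- The only upper limit is the end-of-study date.

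Medication start dates follow the adverse-event algorithm: 1 January when only the year is known, and the first of the month when only the day is missing. An adverse-event date that lands before Study Day 1 is moved to Day 1, but the SAP adds that "this applies to AE start date imputation only". For adverse events the SAP also relies on a CRF item asking whether the event began before first dose. It names no such item for medications.

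SAP 5.2 derives baseline use from these dates. Vitamin D counts if used in the seven days up to Day 1. Other drugs of interest count if used on Day 1, which includes "medication use that starts prior to Study Day 1 and ends on Study Day 1 or duration of use covers Study Day 1".

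Protocol 7.3.6 creates records of past use: "If the subject is not taking any calcium supplements, phosphate binders, or vitamin D sterols at screening, then the last use should be recorded".

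Baseline vitamin D sterol use, and baseline use of a calcium-containing binder or calcium supplement, are planned covariates in SAP 4.1. They define subgroups (SAP 4.2 and 9.5.2.1) and are candidates for the multiple-imputation sensitivity models (SAP 4.1, Table 9-1 and 9.5.2.2). SAP 9.6.9 tabulates use of these drugs at baseline and on study.

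**The concern.** Widest-window imputation is a normal default when nothing else is known about a drug. Here something else may be known: that the subject was not taking it at screening, or that it was started after dosing began. As written, the rule can override that fact.

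The two directions have different effects. A past drug carried forward makes a non-user both a baseline user and an on-study user. An on-study start moved back makes a genuine on-study user a baseline user as well, so only the baseline status is wrong.

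The second error also puts post-randomisation information into a variable labelled baseline. Protocol 6.2.3.2 lets investigators raise oral calcium, or start active vitamin D, when corrected calcium is below 8.3 mg/dL. Some of these starts are therefore a response to treatment.

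**Working it through.** The documents give no figure on this point, so there is none to reproduce. The check applies the SAP 8.3 rules as written and compares the result with SAP 5.2.

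**Worked example.** Assume Day 1 is 10 June 2019 and end of study is Day 1 + 182 + 30 days, which is 8 January 2020.

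| Record | Imputed date | Result |
|---|---|---|
| Past drug, stop missing | 8 Jan 2020 | baseline user, and on study throughout |
| Past drug, stop 2019 | 31 Dec 2019 | baseline and on-study user |
| Past drug, stop June 2019 | 30 Jun 2019 | baseline and on-study user |
| Past drug, stop May 2019 | 31 May 2019 | not carried in |
| Past drug, stop 2018 | 31 Dec 2018 | not carried in |
| On-study start, 2019 | 1 Jan 2019 | baseline user if the stop is on or after Day 1 |
| On-study start, June 2019 | 1 Jun 2019 | baseline user if the stop is on or after Day 1 |
| On-study start, July 2019 | 1 Jul 2019 | not moved before Day 1 |

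**Shares.** Assume Day 1 is uniform over 365 days. Let g be the true gap in days between Day 1 and the stop (or start).

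- *Stop fully missing:* always carried to end of study, so 100% at any gap.
- *Year only:* misclassified when both dates fall in the same calendar year, so the share is (365 − g)/365. For a past stop at g = 56 this is 309/365 = 85%; at g = 180 it is 185/365 = 51%; at g = 365 it is 0.
- *Day missing:* misclassified when both dates fall in the same month, so the share is Σ max(0, Lₘ − g)/365 over the twelve month lengths Lₘ. At g = 10 this is (7×21 + 4×20 + 18)/365 = 245/365 = 67%. At g = 20 it is (7×11 + 4×10 + 8)/365 = 125/365 = 34%. At g = 30 it is 7/365 = 2%.

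**Averages over evenly spread gaps.**

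- Past stops 8 to 365 days before Day 1 (358 gaps), day missing: (7×276 + 4×253 + 210)/(365×358) = 3,154/130,670 = 2.4%.
- Past stops over the same range, year only: 1 − 186.5/365 = 48.9%.
- On-study starts 1 to 182 days after Day 1, day missing: (7×465 + 4×435 + 378)/(365×182) = 5,373/66,430 = 8.1%. Starts more than 30 days after Day 1 contribute nothing.
- On-study starts over the same range, year only: 1 − 91.5/365 = 74.9%.

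These shares are for use on Day 1 itself. The seven-day vitamin D window makes the past-stop shares somewhat larger: for a day-missing stop 20 days before Day 1, 57% rather than 34%.

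**Where it reaches.** SAP 9.5.1.1 and 9.5.2.1 stratify the primary analysis and the key secondary tests by screening PTH, screening corrected calcium and country only. Neither uses a medication variable.

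**The case against.** - **Past-use records may be outside the rule.** SAP 5.3 takes drugs of interest from the concomitant-medication CRFs, and Protocol 6.5 collects concomitant therapy from consent onward. Last use before consent is medication history, in its own section (7.3.6). Table 2 has one combined row for prior and concomitant medication, but that schedules visits and does not show a single dataset. This stands: the past-use half is conditional. Drugs stopped between consent and Day 1 are in scope either way, but should be few, because inclusion criteria 106, 108 and 109 require stable dosing through randomisation.
- **The large percentages could be read as expected error rates.** They are not. The 49% and 75% figures apply only to year-only dates. Medication use is recorded at every visit, so an on-study start known only to the year is unlikely after queries. The day-missing figures (2.4% and 8.1%) are the more realistic ones.
- **A reader might infer a treatment-related bias of real size.** Decreased blood calcium was commoner on etelcalcetide than on cinacalcet in the earlier head-to-head study (68.9% against 59.8%, Protocol 2.2.1). Those are adverse-event rates from a 26-week study, not early medication starts. Under Protocol 6.2.3.2 active vitamin D is for use when other measures fail. The direction is plausible, but the documents give no basis for a size.
- **A reader might infer that past cinacalcet would wrongly exclude subjects from the per-protocol set.** SAP 6.3 frames those exclusions as deviations, and SAP 8.4 has the list of important deviations finalised before unblinding. Nothing says they come from imputed dates, so that reading is not supported.

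None of this removes the gap in SAP 8.3. No other section bounds an imputed medication date by known status.

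**Conclusion.** The point holds, with limited reach. A fully missing stop always carries a past drug to end of study. A partial stop does so only when its known part reaches the year or month of Day 1. A partial start is moved to or before Day 1 only when its known part matches that of Day 1. It would be too strong to say that past drugs with partial dates are generally carried into the study, or that on-study starters are wrongly counted as on-study users.

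The effect is on baseline vitamin D sterol use and calcium or binder use in the subgroup analyses, the multiple-imputation sensitivity models and the medication tables. The main confirmatory results do not depend on it. The size rests on two unknowns: how many dates stay incomplete after queries, and whether Protocol 7.3.6 history is held with the concomitant-medication data. The percentages also assume an even spread of Day 1 and of gaps. The change is worth making because it is cheap and the present rule can contradict recorded facts.

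**What to change.** In SAP 8.3, bound imputed medication dates by recorded status:

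1. For a drug recorded as last used before screening, cap the imputed stop at the day before informed consent. For one recorded as stopped during screening, before first dose, cap it at the day before Study Day 1. Class the subject as a baseline non-user of that drug. Keep the end-of-study default for all other fully missing stops.
2. For a drug recorded as started on study, and not merely first reported late, do not let the imputed start fall before the day after Study Day 1.

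One detail needs a sentence. SAP 5.2 counts vitamin D over the seven days up to Day 1, so a cap at the day before Day 1 still falls inside that window. The SAP should say how a vitamin D product stopped during screening is classed when its partial date leaves those seven days open.

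The SAP should also state whether Protocol 7.3.6 records are in the data to which these rules apply, and which recorded item shows prior or on-study status. The medication fields listed in Protocol 6.5 include no such flag, so it may have to be taken from the medication history and visit records. Where status is not recorded, the present rules stay.

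The cost is a few lines of SAP text and minor programming. A few records with truly unknown dates would no longer be given the widest window.
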